11.3.3.2 Secondary Efficacy Endpoints

The same properties of the primary and secondary estimand of the primary endpoint will be considered for each of the secondary endpoints. For responder analyses, the between-group difference in proportions (Xlucane v Lucentis[®]) will be of interest.

The following continuous secondary endpoints will be analyzed in a similar fashion to the primary efficacy endpoint:

- Change in BCVA letters at Week 4, Week 12, Week 16, Week 24, Week 36 and Week 52 compared to Baseline using the ETDRS protocol
- Change in total size of choroidal neovascular leakage area in the study eye measured by FA at Week 24 and Week 52 compared to Baseline
- Change in total size of choroidal neovascularization in the study eye measured by FA at Week 24 and Week 52 compared to Baseline
- Change in Central Foveal Thickness (CFT) in the study eye measured by OCT at Week 2, Week 4, Week 8, Week 16, Week 24, Week 36 and Week 52 compared to Baseline
- Changes in the size and/or number of intraretinal cystoid space (cysts), subretinal fluid, and retinal pigment epithelium detachments in the study eye measured by qualitative morphology-based OCT

The following secondary endpoints will be analysed (stratified by randomization stratification group) using a Cochran-Mantel-Haenzel test and Miettinen-Nurminen methods to obtain the difference in proportions between groups and corresponding 90% and 95% CIs.

- Percentage of subjects with loss of <15 letters using ETDRS, evaluated as change at Week 4, Week 8, Week 24, and Week 52 compared to Baseline in the study eye
- Percentage of subjects with gain of ≥ 15 letters using ETDRS, evaluated as change at Week 4, Week 8, Week 24, and Week 52 compared to Baseline in the study eye
- Percentage of subjects without intra- or subretinal fluid in the study eye (ie, completely dry) at Week 24 and Week 52
- Percentage of subjects with retinal pigment epithelium detachments in the study eye

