4. Dilated fundus examination of the posterior segment is conducted in both eyes at Screening and prior to Randomization on Day 0. At all other scheduled visits dilated fundus examination is conducted in the study eye only.
5. IOP is measured in both eyes at Screening, prior to Randomization on Day 0, and at Week 52 (or EOT visit). At all other scheduled visits, IOP is measured in the study eye only. At pre-injection, IOP should be measured using the Goldmann tonometry method. After IVT injection (eg, 30 minutes post injection), non-contact tonometry may be used, but in the event IOP is greater than 36 mm Hg, it is recommended to perform IOP measurement with Goldmann or Tonopen or ICare (applanation tonometer) within the next 30 minutes.
6. CFP assessment is conducted in both eyes at Screening. At Week 24 and 52 (or EOT visit), CFP assessment is conducted in the study eye only. Images should be sent to the CRC.
7. FA assessment is conducted at Screening, Week 24 and 52 (or EOT visit), Images of both eyes should be sent to the CRC for these visits. FA Grading by CRC is conducted on both eyes at Screening Visit and in the study eye only at Week 24 and 52 (or EOT visit).
8. Assessments to be confirmed by the CRC during Screening and prior to Randomization.
9. OCT assessment is conducted in both eyes at Screening and BL. At all other visits, including Week 52 (or EOT visit), OCT assessment is conducted in the study eye only. Images should be sent to the CRC.
10. BCVA assessment by ETDRS at 4 meters, including manifest refraction.
11. Vital signs measurements to include heart rate and blood pressure. Systolic and diastolic blood pressure and pulse rate will be measured after patients have been at rest (seated) for at least 5 minutes.
12. Hematology panel evaluations will be sent to a central laboratory. See also [Section 10.1.4.2.3](#). Results from Screening visit must be reviewed by the investigator before patient is randomized

13. Clinical chemistry panel evaluations will be sent to a central laboratory. See also [Section 10.1.4.2.3](#). Results from Screening must be reviewed by the investigator before patient is randomized

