12. Spherical equivalent of the refractive error in the study eye demonstrating more than 8 diopters of myopia.
13. Corneal transplant or corneal dystrophy in the study eye.
14. History of rhegmatogenous retinal detachment in the study eye.
15. History of macular hole in the study eye.
16. Retinal pigment epithelial tear or rip involving the macula in the study eye as assessed by FA and confirmed by the central reading center.
17. Current vitreous hemorrhage in the study eye.
18. Subretinal hemorrhage that is \geq 50% of the total lesion area in the study eye, or if the subretinal hemorrhage involves the fovea is 1 or more DA ($\geq 2.54 \text{ mm}^2$) in size in the study eye, as assessed by FA and confirmed by the central reading center.

19. Other intraocular surgery (including cataract surgery) in the study eye within the 3 months prior to Baseline. The yttrium aluminum garnet [YAG] posterior capsulotomy is allowed no later than 4 weeks prior to Screening.
20. Any concurrent intraocular condition in the study eye (eg, cataract or diabetic retinopathy) that, in the opinion of the investigator, could require treatment during the study period to prevent or treat loss of visual acuity.
21. Significant media opacities (including cataract) in the study eye interfering with BCVA assessment or fundus imaging (FA/FP/OCT).
22. Aphakia or absence of the posterior capsule in the study eye, unless it occurred as a result of a YAG posterior capsulotomy in association with prior posterior chamber intraocular lens (IOL) implantation.
23. Presence of advanced glaucoma or optic neuropathy that involves or threatens the central visual field in the study eye (as judged by the investigator).
24. History of glaucoma filtering surgery or ALT in the study eye (Exception: Laser iridotomy and SLT are allowed).
25. Uncontrolled ocular glaucoma or hypertension in the study eye, defined as IOP \geq 25 mm Hg despite treatment with anti-glaucoma medication.
26. Any previous systemic anti-VEGF treatment (eg, bevacizumab).
27. Contraindication for Lucentis[®] (hypersensitivity to ranibizumab or to any of the study treatment excipients).
28. Current treatment for active systemic infection.

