8.4.3 Randomization

The receipt and review of the lab report is necessary before randomizing a subject. Upon confirmation of eligibility for a given subject to participate in the study, a unique randomization number for that subject will be assigned via an IWRS. The IWRS will be accessed immediately by study site personnel after confirmation of the subject's eligibility has been recorded. The randomization number for a given subject will be used to identify the study drug that will be administered to that subject.

The randomization scheme will automatically ensure that the study drug assignment for a given subject is random and that an overall 1:1 ratio of assignments to each of the 2 study drug treatments is approximated.

In addition, the randomization scheme will include the following stratification parameters to ensure balanced distribution of assignment to the 2 treatments: eye color (light iris vs dark iris), geographical region where enrolled and the BCVA letters at Baseline (55 or lower, 56 to 65, 66 or higher). Permuted random blocks within each stratification combination will be used to ensure the 1:1 ratio within each combination.

An independent biostatistician will create the randomization scheme, which will remain unavailable to all other masked individuals, until after study completion and subsequent locking of the study database.

Once a randomization number has been assigned, that number must not be used again for any other subject (eg, when a subject is withdrawn from the study, that subject's randomization number must not be used again for any other subject).

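### The percentage of subjects with RPE detachment is compared without adjusting for detachment status at entry, which loses precision but does not bias the result

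*Combined protocol and SAP*

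**What the plan says.** Section 11.3.3.2 puts "Percentage of subjects with retinal pigment epithelium detachments in the study eye" last among four binary secondary endpoints. The other three name their visits; this one names none and makes no reference to baseline. All four are to be "analysed (stratified by randomization stratification group) using a Cochran-Mantel-Haenzel test and Miettinen-Nurminen methods", giving the "difference in proportions between groups and corresponding 90% and 95% CIs". No margin is attached.

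Section 8.4.3 defines the strata as "eye color (light iris vs dark iris), geographical region where enrolled and the BCVA letters at Baseline", with BCVA in three groups. Detachment status is not among them.

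The eligibility criteria (sections 8.3.2 and 8.3.3) do not mention RPE detachment. The nearest exclusion is "Retinal pigment epithelial tear or rip involving the macula in the study eye", which is a different finding. Status before treatment can be known: note 9 to the schedule in section 8.1.1 says "OCT assessment is conducted in both eyes at Screening and BL" and that images go to the reading center.

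The continuous list in section 11.3.3.2 has a related endpoint on how the size or number of RPE detachments changes. Section 11.1 leaves technical details to a SAP to be finalized before the interim unmasking. The text supplied contains no further analysis of the percentage endpoint.

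**The concern.** This is the only one of the four binary endpoints whose own status can vary at entry and is not used. The two letter-response endpoints are defined as changes from baseline and stratified by baseline BCVA group. The endpoint for eyes free of fluid starts near zero, because inclusion criterion 3 requires intra- or subretinal fluid. The continuous endpoints follow the primary model, which includes the baseline value.

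An eye with a detachment at entry is likelier to have one later than an eye without. If so, part of the spread in the unadjusted difference comes from which eyes happened to be allocated where, and not from the products. In a biosimilarity trial the anatomical endpoints support the claim of similarity. At stake is how sharply this one can do so, and how far its estimate moves when the arms differ by chance at entry.

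**Working it through.** The plan gives no figure for this endpoint. Its only power statement (section 11.4) concerns the primary endpoint and does not bear on this point. It was reproduced only to check the sample-size inputs: with 290 per arm, SD 10, margin ±3.5 letters and a true difference of zero, SE = 10 × √(2/290) = 0.830. Power for the 95% interval is then 2Φ(3.5/0.830 − 1.96) − 1 = 97.6%, consistent with the stated >90%.

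**Inputs**
- 580 randomized (section 11.4), with "Permuted random blocks within each stratification combination will be used to ensure the 1:1 ratio within each combination" (section 8.4.3): n = 290 per arm, all taken as evaluable.
- Assumed, because the documents give no rates: baseline prevalence b = 0.30-0.80; probability p1 = 0.40-0.90 of a detachment at follow-up if present at baseline; probability p0 = 0.02-0.10 if absent.

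**Formulas**, with p = b·p1 + (1 − b)·p0:
- Unadjusted 95% half-width = 1.96 × √[2p(1 − p)/n].
- Half-width adjusted for baseline status = 1.96 × √{2[b·p1(1 − p1) + (1 − b)·p0(1 − p0)]/n}.
- SD of the chance difference in baseline prevalence = √[2b(1 − b)/n]. Each point of it moves the unadjusted difference by (p1 − p0) points.

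**Worked example: b = 0.6, p1 = 0.8, p0 = 0.05**
- p = 0.48 + 0.02 = 0.50, so p(1 − p) = 0.25.
- Within baseline groups: 0.6 × 0.16 + 0.4 × 0.0475 = 0.115.
- Unadjusted: 1.96 × √(2 × 0.25/290) = 8.1 points.
- Adjusted: 1.96 × √(2 × 0.115/290) = 5.5 points, about 32% narrower.
- Chance baseline imbalance: 1.96 × √(2 × 0.6 × 0.4/290) = ±8.0 points, carried through as 8.0 × 0.75 = ±6.0 points.
- The lost precision and the carried imbalance are one quantity: 0.115 + 0.75² × 0.24 = 0.115 + 0.135 = 0.25.

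**Range over the assumed rates**

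| b | p1 | p0 | Unadjusted (±points) | Adjusted (±points) | Narrower by |
|---|---|---|---|---|---|
| 0.3 | 0.9 | 0.02 | 7.34 | 3.28 | 55% |
| 0.5 | 0.8 | 0.05 | 8.05 | 5.24 | 35% |
| 0.7 | 0.4 | 0.05 | 7.42 | 6.95 | 6% |
| 0.8 | 0.4 | 0.10 | 7.71 | 7.46 | 3% |

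A 5-point baseline imbalance moves the unadjusted difference by 5 × 0.30 = 1.5 to 5 × 0.88 = 4.4 points.

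**Simulation** (20,000 trials, no true difference, rates of the worked example): mean half-widths were 8.1 points unadjusted and 5.5 points stratified on baseline status. The unadjusted difference moved 0.74 points per point of imbalance and the stratified one essentially none (−0.008). Coverage was 95% for both.

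**The case against.** The strongest reply is that nothing here is wrong, only less precise than it could be. Randomization makes the unadjusted comparison valid, and its interval already allows for chance imbalance. That stands, and the simulated coverage confirms it. A reader might infer that an imbalance would make the inference invalid; the design does not support that.

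The size of the gain rests wholly on assumed rates. That also stands. A reader might infer that later prevalence mostly reflects baseline prevalence, but no passage says so, and with 40% persistence the gain can be as little as 3%.

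A reader might also infer that the plan never looks at change in detachments. It does, through the separate endpoint on their size or number, though that endpoint does not adjust the percentage comparison. Section 11.1 promises data by treatment group and visit, so an imbalance at entry may be visible; seeing it does not remove it from the estimate.

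Finally, no decision hangs on this endpoint, and analysing by the randomization strata matches the design. Both are true. The second argues against dropping strata to make room for baseline status, but not against adding baseline status to a model that keeps the randomization factors.

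**Conclusion.** The point holds as a loss of precision in one secondary endpoint. Over the assumed rates the 95% interval would be about 3% to 55% narrower with adjustment, and ±8.1 against ±5.5 points at 60% prevalence, 80% persistence and 5% new detachment. The calculation assumes 290 evaluable eyes per arm and ignores whatever the existing strata already absorb. It also takes the comparison to be at a follow-up visit, which the plan does not name; the missing visit is a gap in its own right.

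It would be wrong to read this as bias, or as a threat to the biosimilarity conclusion. That conclusion rests on Week 8 BCVA under the primary estimand (section 11.3.3.1), which this does not touch.

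**What to change.** For this endpoint, in section 11.3.3.2 and the SAP and before the interim unmasking:

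- Estimate the difference in proportions as a standardized (marginal) risk difference from a logistic model with baseline RPE-detachment status (present or absent on the pre-treatment OCT) and the randomization factors, with 90% and 95% intervals.
- State the visits, for example Weeks 24 and 52, as for the fluid-free endpoint.
- Show descriptively the numbers resolved among eyes with a detachment at baseline and the numbers new among eyes without. These are subsets and should not carry the comparison: in the worked example, 0.6 × 290 = 174 eyes per arm with 20% resolved give a half-width of 1.96 × √(2 × 0.2 × 0.8/174) = 8.4 points.

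There is no need to drop region or eye color. Fully crossing the strata with baseline status would give 2 × 3 × 2 = 12 cells per region, which could be sparse; a model with main effects avoids that.

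The cost is a change of wording, a method slightly different from the other binary endpoints, and a little more analysis. No new data are needed, because baseline detachment is already required for the size and number endpoint.

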11.3.4 Safety Endpoints

11.3.4.1 Adverse Events

Events that occur after a patient provides informed consent but before the time of the first dose of study drug will be considered non-treatment-emergent adverse events (AEs). Treatment-emergent AEs (TEAEs) are defined as events that are newly occurring or worsening from the time of the first dose of study drug.

Reported AE terms will be coded using Medical Dictionary for Regulatory Activities (MedDRA) preferred terms and system organ classes (SOCs).

The percentage of patients with TEAEs together with the number of the respective TEAEs overall, by SOC, and by preferred terms within each SOC will be presented. Separate summaries will be provided for overall TEAEs, TEAEs by severity,

treatment-related TEAEs, serious TEAEs, and TEAEs leading to treatment discontinuation.

All AEs will be presented in patient listings.

11.3.4.2 Other Safety Endpoints

The following endpoints (as well as the change from Baseline when applicable) will be summarized:

- Injection site reactions
- Vital signs (heart rate, systolic blood pressure, diastolic blood pressure)
- Clinical chemistry (creatinine, AST/SGOT, ALT/SGPT, alkaline phosphatase, lactate dehydrogenase (LDH), total bilirubin, albumin, total protein, sodium, potassium, chloride, glucose, uric acid, total cholesterol, triglycerides, calcium, and phosphorus)
- Immunogenicity (ie, anti-ranibizumab antibodies and NAb)

11.3.5 Pharmacokinetics

The PK data analysis will be performed using the PK Set.

The ranibizumab PK concentrations will be summarised by treatment and listed individually. Descriptive statistics on the PK parameters ($C0$, predose; $C1$, time point 23 hours [\pm 60 minutes] after the first dose on Day 1; and $C6$, time point 23 hours [\pm 60 minutes] after the sixth dose on Week 20) will be presented. If a difference in ranibizumab protein concentration between Xlucane and Lucentis® batches is detected, additional descriptive statistics will be presented taking such difference into account. Further details will be defined in the statistical analysis plan.

11.3.6 Interim Analyses

When all subjects have completed their 6-month assessments, an *unmasked* analysis of efficacy and safety endpoints as well as PK and immunogenicity will be performed. The aim of the *unmasked* analysis is to initiate the submission of the application for marketing authorization as agreed with the European Medicines Agency. This analysis will not affect the further conduct of the study.

11.3.7 Handling of Missing Data

Any data following an IE, which is deemed to have been impacted by the IE, may be treated as missing data in the analysis in accordance with [Section 11.3.3.1](#).

For the primary analysis of each endpoint/estimand, a missing at random (MAR) approach will be assumed for missing data (ie, the probability of an observation being missing depends only on observed measurements). Sensitivity analyses will be conducted using different missing data assumptions such as missing not at random (MNAR) and missing completely at random (MCAR) within each endpoint/estimand.

For continuous endpoints, a MMRM model will be used (using only evaluable data) to adopt a MAR assumption for the primary analysis. Patients with missing data at a particular time point still contribute to the analysis at that time point based on their other observed data used in the MMRM (ie, visit, treatment, baseline BCVA letter score, geographical region of the country where enrolled, eye color (light iris vs dark iris), and BCVA letter score at other visits) and the known covariance structures between these factors. The sensitivity analyses will use alternate methods (to be detailed in the SAP) of imputing missing data such as multiple imputation with pattern mixture modelling and using evaluable data only. ANCOVA models will be used to analyze such data at the respective visit.

For non-continuous endpoints, alternate methods will be specified in the SAP to impute missing data, although the same mechanisms will be assumed as for continuous endpoints (ie, primary analysis assumes MAR, sensitivity analyses to assess MNAR and MCAR).

Due to the indication under evaluation in this study, it is considered that most missing data due to COVID-19 can be treated as MAR, but this will be evaluated and agreed at the BDRM. Additional subgroup and sensitivity analyses relating to the potential bias from missing data and/or deviations from the protocol during the COVID-19 pandemic will be considered for analysis of all endpoints and added to the SAP prior to database lock.

11.4 Determination of Sample Size

The change in BCVA after 8 weeks was evaluated from previous studies based on similar patient populations. There was a wide range of SD across the studies, ranging from 8.58 letters to 11.83 letters.

For the purpose of sample size calculation, an SD of 10 letters will be assumed for this study. This is based on an analysis of the data from clinical trials of the originator product demonstrating a clear correlation between baseline BCVA and the SD of the change of BCVA at Week 8. Considering that a narrower inclusion criterion for BCVA is being applied in this study compared to the studies of the originator product, it is expected that a baseline BCVA of around 60 letters will be observed. Therefore, an SD of 10 for the primary endpoint is well in the upper range of what is expected.

From 580 randomized patients there will be >90% power to show equivalence (ie, two-sided 95% CI for the mean difference between Xlucane and Lucentis® is confined within the equivalence margin of ± 3.5 letters) if the SD is no more than 10.

The power calculations were performed using SAS® (Version 9.3, SAS Institute Inc., Cary, NC, USA).

11.5 Protocol Deviations

All protocol deviations related to study inclusion or exclusion criteria, conduct of the study, subject management, or subject assessment will be identified, evaluated, and closed prior to the respective database lock (interim or final analysis) and will be described in the final SAP/clinical study report.

12 QUALITY ASSURANCE AND QUALITY CONTROL

12.1 Audit and Inspection

Study centers and study documentation may be subject to Quality Assurance audit during the course of the study by the Sponsor or its nominated representative. In addition, inspections may be conducted by regulatory authorities at their discretion.

12.2 Monitoring

Data for each subject will be recorded on an eCRF. Data collection must be completed for each subject who signs an informed consent form (ICF) and is administered study drug.

In accordance with current GCP and ICH guidelines, the study monitor will carry out source document verification at regular intervals to ensure that the data collected in the eCRF are accurate and reliable.

The investigator must permit the monitor, the IEC/IRB, the Sponsor's internal auditors, and representatives from regulatory authorities direct access to all study-related documents and pertinent hospital or medical records for confirmation of data contained within the eCRFs.

12.3 Data Management and Coding

Syneos Health will be responsible for activities associated with the data management of this study. This will include setting up a relevant database and data transfer mechanisms, along with appropriate validation of data and resolution of queries. Data generated within this clinical study will be handled according to the relevant standard operating procedures (SOPs) of the data management and biostatistics departments of Syneos Health.

Study centers will enter data directly into an electronic data capture (EDC) system by completing the eCRF via a secure internet connection. Data entered into the eCRF must be verifiable against source documents at the study center. Data to be recorded directly on the eCRF will be identified and the eCRF will be considered the source document. Any changes to the data entered into the EDC system will be recorded in the audit trail and will be FDA CFR 21 Part 11 compliant.

Medical coding will use Medical Dictionary for Regulatory Activities (MedDRA) for concomitant diseases and AEs and WHO Drug Dictionary for medications.

Missing or inconsistent data will be queried in writing to the investigator for clarification. Subsequent modifications to the database will be documented.

